9. PHARMACODYNAMIC ASSESSMENTS

9.1. Evaluation of Response to ID Capsaicin

The response to ID injection of capsaicin will be assessed in 6 ways; subjective rating of pain, area and pain score of hyperalgesia, area and pain score of brush-evoked allodynia and AF. Measurements will be taken prior to (within 15 minutes) and at the 15-, 30-, 60-, 90- and 120-minutes time points post injection. Prior to each injection, 4 intersecting lines forming 45-degree angles will be drawn on the skin using a fine-tipped skin marker for assessment of areas of hyperalgesia and allodynia. The 4 lines will intersect at the injection site and will be marked in 1cm graduations starting from the intersection.

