10.5.4.2. Modelling

Two separate sets models will be fit to the data. Individual models will be fit per treatment group to assess means and change from baseline in score and area for each PD parameter. Combined models will be fit using all treatment groups to assess differences in means and change from baseline in score/area against placebo.

Model Group 1:

The MMRM model will contain a term for timepoint and will contain baseline Score / Area as a covariate and subject as a random effect. An unstructured covariance matrix will be assumed.

If the fit of the unstructured covariance structure fails to converge, the following covariance structures will be tried in order until convergence is reached: toeplitz with heterogeneity, autoregressive with heterogeneity, toeplitz, and autoregressive.

Least squares (LS) means will be reported for each visit along with corresponding 95% confidence intervals (CIs).

The model will be fit separately for each treatment group, for the following dependent variables:

- A) Score / Area for each PD parameter
- B) Change in score / Area for each PD parameter

Model Group 2:

The MMRM model will contain terms for randomised treatment group and timepoint and will contain baseline Score / Area as a covariate and subject as a random effect. An unstructured covariance matrix will be assumed.

If the fit of the unstructured covariance structure fails to converge, the following covariance structures will be tried in order until convergence is reached: toeplitz with heterogeneity, autoregressive with heterogeneity, toeplitz, and autoregressive.

Least squares (LS) means will be reported by visit for each randomised treatment group; the difference in LS means between each dose arm and placebo will be presented along with corresponding 95% CIs.

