2.2. Part B

Part B is a randomised, double-blind, placebo-controlled parallel group study to investigate single oral doses of KLS alone or KLS-GABA compared to 300 mg gabapentin alone or placebo, in healthy male subjects using the ID capsaicin model.

It is planned to enrol 128 subjects randomised evenly to 8 possible treatments; subjects will receive either KLS alone, KLS-GABA, 300 mg gabapentin or placebo.

The planned treatments are:

- KLS alone (40 mg, 80 mg or 160 mg)
- KLS-GABA (40 mg-17mg, 80 mg-34 mg, or 160 mg-68 mg)
- Gabapentin* (300 mg)
- Placebo

* Product commercialised in the UK: Neurontin 300 mg hard capsules.

Subjects will be required to attend the CRU for a screening visit within 28 days prior to dosing to ensure they meet the inclusion/exclusion criteria and are in good general health.

Statistical Analysis Plan

Following initial screening, subjects will be required to attend the CRU for an additional screening visit at least 7 days prior to first dosing to assess their response to capsaicin and familiarise them in the pain measurements. Subjects will receive a single ID administration of 100 µg capsaicin into a novel site on the volar surface of the forearm. Prior to and 15 minutes after administration of capsaicin, measurements of pain, hyperalgesia, allodynia and AF will be performed according to the procedures described in Section 9. In order for the subjects to be eligible, they must be able to tolerate the injection and also demonstrate a sufficient response, defined as an area of hyperalgesia $\geq 15\text{cm}^2$ 15 minutes after the injection.

Subjects will be admitted to the CRU on Day -1 for collection of baseline safety assessments, pain measurements and to complete the ID capsaicin model (see Appendix 2). Subjects will receive a single 100 µg capsaicin injection into a novel site on the volar surface of the forearm.

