6.8.3. PD Modelling

Two separate sets models will be fit to the data. Individual models will be fit per treatment group ("KLS 40 mg", "KLS 80 mg", "KLS 160 mg", "KLS 40 mg - GABA 17 mg", "KLS 80 mg - GABA 34 mg", "KLS 160 mg – GABA 68 mg", "Gabapentin 300 mg", "Placebo") to assess means and change from baseline in score and area for each PD parameter (see [Section 6.8.1](#)). Combined models will be fit using combined treatments (i.e. different doses of the same treatment combined – "KLS alone", "KLS-GABA", "Gabapentin", "Placebo") to assess differences in means and change from baseline in score and area for each PD parameter (see [Section 6.8.1](#)).

Individual models (by treatment):

The MMRM model will contain terms for the actual treatment group (and timepoint and will contain baseline Score / Area as a covariate and subject as a random effect.

An unstructured covariance matrix will be assumed. If the fit of the unstructured covariance structure fails to converge, the following covariance structures will be tried in order until convergence is reached: toeplitz with heterogeneity, autoregressive with heterogeneity, toeplitz, and autoregressive.

Least squares (LS) means will be reported by timepoint along with corresponding 95% confidence intervals (CIs).

The model will be fit separately for each treatment group, for the following dependent variables:

- Score / Area for each PD parameter
- Change in score / Area for each PD parameter

Combined models (treatment as a term; comparing against placebo):

The MMRM model will contain terms for actual combined treatment group and timepoint and will contain baseline Score / Area as a covariate and subject as a random effect.

An unstructured covariance matrix will be assumed. If the fit of the unstructured covariance structure fails to converge, the following covariance structures will be tried in order until convergence is reached: toeplitz with heterogeneity, autoregressive with heterogeneity, toeplitz, and autoregressive.

LS means will be reported by timepoint for each treatment group; the difference in LS means between each dose arm and placebo will be presented along with corresponding 95% CIs.

The modelling will be conducted separately for the following dependent variables:

Statistical Analysis Plan

- Score / Area for each PD parameter
- Change in score / Area for each PD parameter

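### The PD mixed model pairs a random subject effect with an unstructured covariance; the pair is redundant and could trigger the covariance fallback for no data reason (minor, free to fix)

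*SAP*

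**What the plan says.** SAP 6.8.3 describes two sets of repeated-measures models: one fitted arm by arm ("The model will be fit separately for each treatment group") and one on the combined treatment groups with comparison against placebo. Both descriptions include "baseline Score / Area as a covariate and subject as a random effect". Both then state: "An unstructured covariance matrix will be assumed". Protocol 10.5.4.2 joins the two in consecutive sentences for both of its model groups: "subject as a random effect. An unstructured covariance matrix will be assumed".

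The rule for leaving the unstructured matrix is: "If the fit of the unstructured covariance structure fails to converge, the following covariance structures will be tried in order until convergence is reached". The list is "toeplitz with heterogeneity, autoregressive with heterogeneity, toeplitz, and autoregressive". Failure to converge is the only trigger. Neither document tells the analyst to simplify the model first, and neither gives model code.

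On the data, protocol 9.1 sets the measurements at the "15-, 30-, 60-, 90- and 120-minutes time points post injection". SAP 2.2 says: "It is planned to enrol 128 subjects randomised evenly to 8 possible treatments". SAP section 3 plans no hypothesis tests, so these models deliver LS means, differences and 95% confidence intervals.

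**The concern.** An unstructured matrix already lets every variance and covariance within a subject take its own value. A random subject intercept adds one constant to every entry of that matrix, and the matrix can absorb the constant exactly. The likelihood is therefore flat along one direction: subject variance can be traded against the residual matrix with no change in fit.

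On its own this is untidy rather than harmful. It matters because of the fallback rule. A plan that builds in a singular direction and changes the covariance model when the optimiser fails allows a coding artefact, rather than the data, to choose the structure. The fits are many: six PD parameters, two dependent variables, and eight per-arm models plus one combined model make 6 × 2 × 9 = 108, of which 6 × 2 × 8 = 96 use about 16 subjects each. If some fail spuriously and others do not, arms or endpoints (including the area of hyperalgesia, the Part B primary endpoint in the SAP) would be analysed under different covariance structures for no substantive reason.

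**Working it through.** The plan states no figure on this point, so there is none to reproduce. The check has three steps.

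**Inputs.** Five post-injection times, with gaps of 15, 30, 30 and 30 minutes (protocol 9.1). 128 / 8 = 16 subjects per arm, so the combined groups hold 48 (KLS alone), 48 (KLS-GABA), 16 (gabapentin) and 16 (placebo). The documents give no SDs or correlations; every value below is an assumption.

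**1. Identifiability.** Write the covariance of one subject's five values as V = s²J + R, where s² is the subject variance, J the 5 × 5 matrix of ones and R the specified structure. Unstructured R has 5 × 6 / 2 = 15 parameters. For any V, every s² between 0 and 1/(1′V⁻¹1) leaves R = V − s²J a valid covariance matrix, so s² cannot be estimated, while V can. The rank of the derivative of V with respect to its parameters gives:

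| Structure with random subject effect | Parameters | Rank |
|---|---|---|
| Unstructured | 16 | 15 |
| Heterogeneous Toeplitz | 10 | 10 |
| Heterogeneous autoregressive | 7 | 7 |
| Toeplitz | 6 | 5 |
| Autoregressive | 3 | 3 |

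So the intended structure and the third fallback are redundant, and the first two fallbacks are not. One qualification: heterogeneous Toeplitz has rank 10 when the SDs differ over time, but rank 9 at exactly equal SDs, where it reduces locally to ordinary Toeplitz. In that case an equal-variance structure costs no coverage (step 3).

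**2. Can the redundancy alone stop convergence?** Data were simulated with SDs of 1.2, 1.1, 1.0, 0.9 and 0.7 and correlation 0.7 to the power of the visit lag, and fitted by REML with Newton-Raphson.

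| Fit | One arm, n = 16: failures | Combined, n = 128: failures |
|---|---|---|
| Unstructured alone | 0 of 60 | 0 of 25 |
| With random subject, plain Newton-Raphson | 47 of 60 | 6 of 25 |
| With random subject, generalised inverse for the singular Hessian | 0 of 60 | 0 of 25 |

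The maximised REML criterion with and without the random effect differed by less than 2 × 10⁻⁸. The term adds no fit; whether it causes failure depends on the optimiser. This was a simple optimiser and not SAS, so the counts show that the mechanism exists. They do not predict a rate.

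**3. Cost of a fallback.** Each fallback with the random effect was fitted, in large samples, to assumed covariances with correlation 0.8 per 30 minutes at the real times. Coverage of a nominal 95% interval for a between-group difference at time t is 2Φ(1.96 × √(V_fitted,tt / V_true,tt)) − 1. This allows each timepoint its own treatment contrast.

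| Fallback | SD flat | SD 1.2 to 0.7 | SD 1.5 to 0.5 |
|---|---|---|---|
| Heterogeneous Toeplitz | 0.94 to 0.96 | 0.94 to 0.96 | 0.94 to 0.96 |
| Heterogeneous autoregressive | 0.94 to 0.96 | 0.94 to 0.96 | 0.94 to 0.96 |
| Toeplitz or autoregressive | 0.95 | 0.89 (15 min) to 0.99 (120 min) | about 0.85 to 1.00 |

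The small departure in the first two rows arises because these structures index correlation by visit lag although the first gap is half the others. The larger departure in the last row comes from forcing one variance on all times.

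**The case against.** **The wording may be loose.** An MMRM normally has one within-subject matrix blocked by subject, and the random-effect phrase may be shorthand for that. This is quite possible. No code settles it, and the text as written specifies both. If shorthand was meant, the correction only clarifies.

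**The results may not change at all.** This stands. V is identified, and software that sets the extra variance to zero or uses a generalised inverse returns the LS means and intervals of the unstructured model.

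**The per-arm models matter least for treatment comparison.** They report within-arm means; placebo differences come from the combined model on about 128 subjects, where stalling was rarer. Dropping one parameter also leaves 15 to be estimated from 16 subjects, so real sparsity remains. Both points are fair. The fix removes the artificial cause of failure, not the genuine one.

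**A stronger reading is tempting.** A reader might infer that the redundancy will push the primary analysis into a structure whose intervals badly miss their nominal coverage. The documents do not support that. The first two fallbacks keep a separate variance at each time and, when SDs differ, are identified with the random effect. Reaching an equal-variance structure would then require two identified models to fail as well, which the redundancy does not explain. Nor do the documents show that the SD falls over the two hours: protocol 3.3 describes capsaicin-induced hyperalgesia and allodynia lasting up to 8 hours, and the SAP adjusts each time for its own Day -1 value, so residual SDs need not follow any fading of the raw response.

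**Conclusion.** The point holds as a minor defect of specification. The redundancy is algebra and needs no assumption: 16 parameters of rank 15 for the intended model, and 6 of rank 5 for the homogeneous Toeplitz fallback. That it can trigger the fallback is a possibility that depends on software, most plausibly in the fits on about 16 subjects.

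The likely consequence, if it happens, is a move of some models to heterogeneous Toeplitz, with nominal 95% coverage of about 0.94 to 0.96. That range rests on the assumed correlation and SD patterns. Figures such as 0.89 to 0.99 apply only if an equal-variance structure is reached and the SDs differ over time as assumed. The effect is on the precision statements of an estimation analysis; no type I error claim is at stake.

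**What to change.** - Delete the random subject effect from both model descriptions in SAP 6.8.3 and from both model groups in protocol 10.5.4.2.
- State that subject is the repeated-measures cluster for the unstructured matrix, and that no separate random effect is fitted.
- State that the fallback list is used only if the unstructured model without the random effect fails to converge.

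In the simulation this model had 15 parameters of rank 15 and converged in 60 of 60 per-arm and 25 of 25 combined fits at the same likelihood, so no information is lost. The cost is a few words in each document and one line of code, best settled before database lock.

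Kenward-Roger degrees of freedom are a reasonable option but are not needed for this point. Uncorrected sandwich standard errors should not be part of the change: in a simple check with 16 subjects, normal data and one baseline covariate, they gave about 91% coverage of an arm mean with normal quantiles and 94% with t on 14 degrees of freedom, a loss at least as large as the one expected at the first fallback.

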3. CONVENTIONS

All summary tables, figures and data listings will be produced using SAS software 9.4 or above.

Summaries will be performed by treatment group, separately for Part A (crossover design) and Part B (parallel design).

Descriptive statistics will be used for all variables, as appropriate. Continuous variables will be summarised by the number of observations, mean, standard deviation, median, minimum, and maximum. For log-transformed data, the geometric mean, coefficient of variation (CV), median, minimum and maximum will be presented. No hypothesis testing will be conducted.

Categorical variables will be summarised by frequency counts and percentages for each category.

For AE summaries, the n and % of subjects with event, as well as the number of events, will be shown.

For all Part A endpoints, the last observation before the first dose of corresponding study treatment will be considered the baseline measurement unless otherwise specified. However, if an evaluable assessment is only available after randomisation but before the first dose of randomised treatment then this assessment will be used as baseline. For Part A, baseline for each treatment period will be defined as last observation before the first dose of study treatment (Period 1 Day -1 and Period 2 Day-1).

For Part B safety and PK endpoints, the last observation before dosing will be considered the baseline measurement unless otherwise specified. However, if an evaluable assessment is only available after randomisation but before the first dose of randomised treatment then this assessment will be used as baseline.

For Part B PD endpoints, the day -1 observation at each post-Capsaicin injection timepoint will be considered the baseline measurement for each corresponding day 1 post-Capsaicin timepoint, i.e., the baseline for day 1 15 minutes post-Capsaicin injection will be the day-1 15 minutes post-Capsaicin injection value. If a day-1 PD value at the 30-minute, 60-minute or 90-minute post-Capsaicin timepoints is missing for a subject, linear interpolation will be used to compute the missing value. If a subject's 120-minute post-Capsaicin value is missing, last observation carried forwards (LOCF) will be used instead. If a subject's 15-minute post-Capsaicin value is missing, next observation carried backwards (NOCB) will be used.

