6.8.1. Descriptive PD analysis

Descriptive statistics will be calculated for absolute value and change from baseline (with baseline defined as the day -1 observation at each post-Capsaicin injection timepoint) for Scores (VAS or NRS) and Area measured (cm²) by visit and by treatment according to treatment period.

The list of PD parameters includes:

- area of hyperalgesia (Primary Endpoint);
- measurement of pain score;
- pain score of hyperalgesia;
- area of allodynia;

Statistical Analysis Plan

- pain score of allodynia;
- area of flare.

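### SAP 6.8.3 enters a time-matched baseline as one covariate without saying at which baseline value the per-timepoint LS means are taken, so within-arm LS means and CIs can be shifted

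*SAP*

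**What the plan says.** SAP section 3 (Conventions) defines the Part B PD baseline by timepoint: "the day -1 observation at each post-Capsaicin injection timepoint will be considered the baseline measurement for each corresponding day 1 post-Capsaicin timepoint". Section 6.8.1 repeats the definition for the descriptive tables: "with baseline defined as the day -1 observation at each post-Capsaicin injection timepoint". The timepoints are 15, 30, 60, 90 and 120 minutes after injection (Protocol 9.1), so each subject carries five baseline values per parameter.

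SAP 6.8.3 then says that the MMRM "will contain baseline Score / Area as a covariate and subject as a random effect". It mentions no baseline-by-timepoint term and no centring. For the individual models, "The model will be fit separately for each treatment group", with both the absolute value and "Change in score / Area for each PD parameter" as dependent variables. The output is: "Least squares (LS) means will be reported by timepoint along with corresponding 95% confidence intervals (CIs". Section 3 names SAS 9.4 or above, but no LS-means options are given. The combined models pool doses within KLS alone and within KLS-GABA, and report differences from placebo.

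**The concern.** An LS mean is a prediction at a chosen covariate value. For an ordinary baseline, with one value per subject, the overall mean is a natural choice. Here the covariate changes with time within a subject. Its mean over all records mixes five timepoints and may be typical of none of them. The 15-minute LS mean would then describe a Day -1 response that does not belong to 15 minutes, and likewise at the other times.

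The individual models are there to estimate means and change from baseline in each of the eight arms. They are the only models in the SAP whose named groups are single doses, and they include the primary variable, area of hyperalgesia. They contain no placebo contrast in which a shared shift could cancel. An arm with no drug effect, placebo included, could therefore show a modelled change at some timepoints with a CI that excludes zero too often. Its LS-mean changes could also disagree with the descriptive changes of section 6.8.1, with nothing in the SAP to explain why.

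**Working it through.** The plan gives no figure to reproduce. There is no SD, no Day -1 profile, no slope and no formal sample size calculation (Protocol 10.2). The design inputs are five timepoints (Protocol 9.1) and 128 / 8 = 16 subjects per arm (SAP 2.2). All profiles, SDs and correlations below are assumptions.

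**Identity.** Take one arm with complete data, a separate effect for each timepoint and one common slope. The fitted mean at time t equals the observed mean:

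Ybar_t = alpha_t + beta x Bbar_t.

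The LS mean at the overall covariate mean Bbar is

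alpha_t + beta x Bbar = Ybar_t + beta x (Bbar - Bbar_t).

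If b is the slope of Day 1 on Day -1, then beta = b for the score and beta = b - 1 for the change. Hence:

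- LS-mean change minus mean change = (b-1)(Bbar - Bbar_t)
- LS-mean score minus mean score = b(Bbar - Bbar_t)

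For 0 < b < 1 the two shifts have opposite signs. Each sums to zero over the five timepoints. Each is zero wherever Bbar_t = Bbar, and the shift in change is also zero if b = 1.

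**Worked example.** Assume Day -1 means fall in even steps, 60 / 52.5 / 45 / 37.5 / 30 cm2, so Bbar = 45. With SD 20 on both days, b equals the Day -1/Day 1 correlation.

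- Correlation 0.6: (0.6-1)(45-60) = +6 at 15 min; (0.6-1)(45-30) = -6 at 120 min.
- Correlation 0.8: (0.8-1)(45-60) = +3 at 15 min; (0.8-1)(45-30) = -3 at 120 min.

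**Coverage.** Ignoring the slope's own error, the SE with n = 16 is 20 x sqrt(1 - r^2) / 4. That is 4 for r = 0.6 and 3 for r = 0.8. Shift divided by SE is 6/4 = 1.5 and 3/3 = 1. A nominal 95% t interval on 14 df then covers the true zero change with probability about 0.71 and 0.85 (noncentral t). Simulations with an unstructured covariance gave 0.70 to 0.85 over the two times and the two correlations. With the covariate centred by timepoint, bias was about 0 and coverage 0.90 to 0.96. A slower assumed fall, 60 to 42 cm2, gave shifts of 1.7 to 3.7 cm2 in size and coverage of 0.85 to 0.90.

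**Dependence on the profile.** Shift in LS-mean change, from the identity:

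| Assumed Day -1 means (15/30/60/90/120 min) | b | Shift |
|---|---|---|
| 60/50/40/30/20 | 0.5 | +10/+5/0/-5/-10 |
| 60/50/40/30/20 | 0.9 | +2/+1/0/-1/-2 |
| 60/50/40/30/20 | 1.1 | -2/-1/0/+1/+2 |
| 44/42/40/38/36 | 0.5 | +2/+1/0/-1/-2 |
| 30/45/50/42/33 | 0.5 | -5/+2.5/+5/+1/-3.5 |
| 20/30/40/50/60 | 0.5 | -10/-5/0/+5/+10 |
| 40 throughout | any | 0 throughout |

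**Simulation check.** For a placebo arm of 16 with means 60/50/40/30/20, SD 15, correlation 0.6 and true change 0:

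- LS-mean change at the overall mean: +8.7/+4.0/+0.1/-4.1/-8.9.
- The same model evaluated at each timepoint's own Day -1 mean: +0.2/-0.3/+0.1/+0.1/-0.3, equal to the raw mean change.
- In the combined model, a baseline-by-timepoint term with LS means still at the overall mean: +8.0/+3.8/-0.2/-4.0/-8.0 for placebo. The interaction alone does not remove the shift.
- Combined-model differences from placebo, true values -3/-5/-8: -3.0/-4.7/-7.6 here and -2.9/-4.9/-7.8 with a flat profile. The gap is within simulation error. The shift is the same in every group of that model and cancels.

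**The case against.** The case against acting has several strands.

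*The evaluation point is inferred.* The SAP names the software but no LS-means option, and the table shells are in a separate document. This stands, but the omission is the gap. The shift follows if the text is implemented with the usual default, and nothing in the SAP rules that out.

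*The direction is not known.* A reader might infer a spurious rise early and a spurious fall late in every arm. The documents do not support that. Protocol 3.3 says only that hyperalgesia and allodynia can last up to 8 hours, while all readings fall within two hours. A response that rises and then falls gives a spurious fall at 15 minutes, and a rising one reverses the signs. The six PD parameters need not share a shape. A time-matched baseline suggests that the response may vary with time, but not that it declines.

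*Not every timepoint is affected.* A reader might also infer distortion throughout. The identity contradicts this: the shift is zero wherever the timepoint mean equals the overall mean.

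*Larger groups.* Coverage would be worse with 48 subjects, the size of the pooled KLS and KLS-GABA groups. But the SAP fits no one-group model of that size; each separately modelled arm has 16.

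*Limited consequence.* The SAP plans no hypothesis tests, no decision rule uses the within-arm CIs, raw changes are tabulated, and a shift shared with placebo could be noticed. This stands and lowers the severity. The combined-model text also mentions dose arms when it describes differences from placebo, so dose-level contrasts may be intended. The groups that it names are nevertheless pooled over dose, which leaves the per-arm models as the only ones clearly specified by dose.

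**Conclusion.** The concern holds, with moderate severity. It is not a must-fix. Followed with the usual default, SAP 6.8.3 gives within-arm LS means and CIs that are shifted wherever the Day -1 mean at a timepoint differs from the mean over all timepoints, except that change is unaffected if b = 1. This matters chiefly in the eight per-arm models; the within-group LS means of the combined models are shifted in the same way.

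The identity is exact for complete data with one common slope. The size is illustrative only. The 3 to 6 cm2 and the coverage of 0.70 to 0.85 rest on the assumed fall from 60 to 30 cm2, SD 20, correlation 0.6 to 0.8 and n = 16. A flatter profile or a slope nearer 1 makes the problem smaller, and a flat profile removes it. The documents do not support reading this as a bias in the comparisons with placebo or in the descriptive changes of section 6.8.1.

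**What to change.** In SAP 6.8.3, for both the per-arm and the combined models:

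1. Subtract from each subject's Day -1 value the Day -1 mean of all PD Set subjects at the same timepoint, and use the result as the baseline covariate.
2. State that all LS means are evaluated at centred baseline = 0.

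The second sentence is needed. Without it, each separately fitted arm would by default be evaluated at that arm's own mean of the centred covariate. Under the assumed SD of 20 and n = 16, that mean has a standard error of up to 20 / sqrt(16) = 5 cm2, so the arms would not share a reference. With both sentences, any remaining gap between an arm's LS mean and its raw mean reflects adjustment for chance baseline imbalance, which is what the covariate is for.

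A baseline-by-timepoint term may be added if different slopes are thought plausible. It is optional and does not replace the centring.

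The cost is one data step, one LS-means option and two sentences in the SAP. Trial conduct does not change. Because the direction of the shift depends on data not yet seen, the evaluation point should be fixed before unblinding.

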10.5.4. Pharmacodynamic Statistical Analysis

Summaries and descriptive statistics will be produced for each PD parameter. This includes Scores (VAS or NRS) / Area measured (cm^2) for each treatment and timepoint, along with change from baseline in Score / Area.

Mixed Model Repeated Measures (MMRM) will be fit to data for each PD parameter using two groups of models. Group 1 will assess longitudinal changes in Scores / Area against baseline. Group 2 will assess differences in Scores / Area between treatments for each timepoint.

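### The between-treatment MMRM has no treatment-by-timepoint term, so it can give only one difference from placebo for all five timepoints, although the protocol wants a difference at each.

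*SAP*

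**What the plan says.** SAP 6.8.3 describes two sets of PD models. For the between-treatment set, "Combined models will be fit using combined treatments": KLS alone, KLS-GABA, gabapentin and placebo, with doses pooled. The terms are "The MMRM model will contain terms for actual combined treatment group and timepoint and will contain baseline Score / Area as a covariate", plus a random subject effect and an unstructured covariance with listed fallbacks. The required output is "LS means will be reported by timepoint for each treatment group", together with differences from placebo and 95% CIs.

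The protocol's counterpart, Model Group 2 in 10.5.4.2, has the same form: "The MMRM model will contain terms for randomised treatment group and timepoint and will contain baseline Score / Area as a covariate". Protocol 10.5.4 gives its purpose: "Group 2 will assess differences in Scores / Area between treatments for each timepoint".

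Three other statements matter:
- **Baseline (SAP 3):** "the day -1 observation at each post-Capsaicin injection timepoint will be considered the baseline measurement for each corresponding day 1 post-Capsaicin timepoint". The covariate therefore varies over time within a subject.
- **Inference (SAP 3):** "No hypothesis testing will be conducted".
- **Size (SAP 2.2):** "It is planned to enrol 128 subjects randomised evenly to 8 possible treatments", which is 16 per arm.

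SAP 8 lists one change from the protocol analyses, the Part B primary endpoint. It does not mention a change of target from by-timepoint to time-averaged differences.

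**The concern.** With treatment and timepoint entered only as main effects, the fitted group profiles are parallel. LS means can still be printed by timepoint and group, but the gap between any group and placebo is the same at every timepoint. The stated model therefore cannot deliver the stated result.

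A constant effect is a strong assumption here. Capsaicin is given on Day 1 at the t_max estimated from Part A, readings run for two hours after it, and a secondary objective is to relate plasma level to pain reduction. An effect that grows or fades over that window is plausible. The model would average it and attach the averaged estimate and CI to each timepoint. Since no hypothesis tests are planned, those estimates and intervals are the result.

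A secondary point concerns the baseline. It is time-matched but enters with one slope, and the SAP does not say at what baseline value the LS means are evaluated. If one overall mean is used, each timepoint's LS mean is displaced by an amount that reflects the Day -1 time course and not the drug.

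**Working it through.** **Inputs from the documents.** Five post-injection timepoints (Protocol 9.1). 128 subjects in 8 equal arms: 128/8 = 16 per arm. With doses pooled, KLS-GABA and KLS each have 3 x 16 = 48, against 16 on gabapentin and 16 on placebo. The documents give no SD, correlation, effect profile or power figure, so there is no planned figure to reproduce and the sizes below rest on stated assumptions.

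**Step 1: algebra.** The stated mean model is E[Y] = mu + tau_g + theta_t + beta x baseline. At a common baseline value, group g minus placebo at time t is

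(mu + tau_g + theta_t + beta x b) - (mu + tau_placebo + theta_t + beta x b) = tau_g - tau_placebo.

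No t remains. The covariance structure and the random subject effect do not enter the mean, so they cannot bring it back.

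**Step 2: simulation check.** 48/48/16/16 subjects, unstructured covariance, time-matched baseline, 400 replicates. The assumed true KLS-GABA minus placebo difference was 0, -2, -5, -8, -10 at the five timepoints. The model as written gave -4.88 at all five. With treatment x timepoint added, the mean estimates were 0.03, -1.82, -5.07, -8.06, -9.84.

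**Step 3: coverage.** Closed form, known covariance V, equal variances, no baseline adjustment:
- estimate = w'delta, with w = V^-1 1 / (1'V^-1 1)
- SE = sqrt((1/n1 + 1/n2) / (1'V^-1 1))
- coverage at timepoint j = Phi(1.96 - b) - Phi(-1.96 - b), with b = (estimate - delta_j) / SE

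V is compound-symmetric or AR(1), with correlation 0.5, 0.7 or 0.85.

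One case in full: 48 v 16, compound symmetry, correlation 0.5, effect 1.0, 0.75, 0.5, 0.25, 0 SD. 1'V^-1 1 = 5/(1 + 4 x 0.5) = 1.667. SE = sqrt(0.0833/1.667) = 0.224. The estimate is 0.5. At 120 minutes b = 0.5/0.224 = 2.24, so coverage = Phi(-0.28) - Phi(-4.20) = 39%.

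Coverage at 15 and 120 minutes, range over all correlations and structures:

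| Assumed effect, 15 to 120 min (SD) | 48 v 16 | 16 v 16 |
|---|---|---|
| 1.0 to 0 | 25–55% | 42–67% |
| 0.75 to 0.25 | 74–85% | 81–88% |
| 0.6 to 0.4 | 92–93% | 93–94% |
| constant 0.5 | 95% | 95% |

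The model reports 0.5 SD at every timepoint in all four rows. In the first row, coverage at 30 and 90 minutes is 74–85% (48 v 16) and 81–88% (16 v 16); at 60 minutes it is 95%.

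**Step 4: precision.** With the interaction, the by-timepoint SE is sqrt(1/n1 + 1/n2): sqrt(1/48 + 1/16) = 0.289 SD and sqrt(1/16 + 1/16) = 0.354 SD. Without it, the SE is 0.19–0.27 and 0.23–0.33 SD.

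**Step 5: baseline evaluation (secondary).** For change from baseline, with LS means taken at the overall baseline mean, shift = slope x (overall mean - timepoint mean). Assume a true change of -5 cm2 throughout and a Day -1 area falling evenly from 60 to 25 cm2 (overall mean 42.5). At slope -0.4 the 15-minute value is -5 - 0.4 x (42.5 - 60) = +2.0, and the 120-minute value is -5 - 0.4 x (42.5 - 25) = -12.0.

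| Day -1 area (cm2) | Slope | LS mean change, 15 to 120 min (cm2) |
|---|---|---|
| 60 to 25 | -0.2 | -1.5 to -8.5 |
| 60 to 25 | -0.4 | +2.0 to -12.0 |
| 60 to 25 | -0.64 | +6.2 to -16.2 |
| 50 to 40 | -0.2 | -4.0 to -6.0 |
| 50 to 40 | -0.64 | -1.8 to -8.2 |
| flat | any | no shift |

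For 60 to 25 cm2, a sign change needs a slope steeper than -5/17.5 = about -0.29.

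A simulation of the 60-to-25 profile (48 v 16, SD 20 cm2, 400 replicates, true placebo change -5, true treatment difference -6) used within-subject correlations of 0.3, 0.6 and 0.8. The fitted slopes were about -0.84, -0.69 and -0.37. Placebo LS mean change ran +9.8 to -19.6, +7.1 to -17.2 and +1.5 to -11.6 at the overall mean, but -4.7 to -5.2 once baseline was centred by timepoint. The treatment difference was -5.9 to -6.2 either way, because the shift is common to all arms and cancels.

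**The case against.** **The interaction may have been intended.** Asking for LS means by timepoint and group suggests so, and a programmer might add it. That is plausible, and the table shells, a separate document, might show it. But neither the SAP nor the protocol contains the term. Adding it later would depart from the written model; leaving it out gives five identical differences.

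**A time-averaged difference is a legitimate target.** The SAP's clause on differences from placebo does not repeat that they are by timepoint, and the SAP model differs from the protocol's in pooling doses and using actual treatment. Against a time-averaged target the estimate would not be wrong. However, neither document declares that target, Protocol 10.5.4 states the other one, and SAP 8 records no change.

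**The low coverage figures need a steep profile.** This stands. They come from assumed effects, and for a mild decline coverage is close to nominal. The 0.5 SD average also assumes equal variances; unequal variances would weight the timepoints differently.

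**The time course is still visible elsewhere.** This is true of the descriptives (SAP 6.8.1), the figures (6.8.2) and the per-arm LS means with CIs. An approximate difference could be formed from the per-arm models, but it would not be adjusted to a common baseline, and it is not planned.

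**The baseline point is minor.** It is: it does not touch the placebo comparison and disappears if the Day -1 response is flat.

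**Conclusion.** The concern holds. That the difference from placebo is constant over time follows algebraically from the stated terms and needs no assumption. It conflicts with the purpose given in the protocol, and the gap is in both documents. How much it matters depends on the unknown effect profile: nothing is lost if the effect is constant, little if it drifts from 0.6 to 0.4 SD, and the early and late intervals are badly misleading if it runs from 1.0 SD to 0. What is lost is the adjusted by-timepoint difference from placebo; the raw time course is not.

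This should be fixed, because it is the only adjusted comparison with placebo for the primary endpoint and the correction is small. The baseline point is conditional on a Day -1 response that is not flat and on LS means being evaluated at one overall mean. It affects only how the LS means read over time.

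**What to change.** In SAP 6.8.3, add treatment x timepoint to the combined model, and state that the treatment-minus-placebo differences and 95% CIs at each timepoint come from those LS means. If a single time-averaged difference is really the target, say so and record it in SAP 8 as a change from the protocol.

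In both model sets, centre the time-matched baseline at its own timepoint mean (across arms in the combined model, within arm in the per-arm models), or state that each LS mean is evaluated at that timepoint's baseline mean. A baseline x timepoint term is optional in the combined model and not needed in the 16-subject per-arm models.

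The cost is SAP wording, one model term and a centring rule. By-timepoint intervals widen: unadjusted SE about 0.29 SD instead of 0.19–0.27 for 48 v 16, and about 0.35 SD instead of 0.23–0.33 for 16 v 16. Design and data collection do not change.
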